9.1 Participant Inclusion Criteria

Candidates for this study must meet ALL of the following criteria:

1. Diagnosed with and candidate for clinically-indicated catheter mapping and ablation procedure for the management of ventricular tachycardia, atrial tachycardia or atrial fibrillation (patients having undergone a previous ablation procedure may be included).
2. At least one episode of the targeted arrhythmia (ventricular tachycardia, atrial tachycardia or atrial fibrillation) must have been documented by ECG, Holter, loop recorder, telemetry, implanted device, or transtelephonic monitoring within 12 months of enrollment.
3. Age 18 years or older.
4. Signed Patient Informed Consent Form (ICF).
5. Able and willing to comply with all pre-, post-, and follow-up testing and requirements.

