Primary Objective	
 Assess safety of the OPTRELL™ catheter for use in mapping in the atria and ventricles. Assess feasibility of the OPTRELL™ catheter for mapping in the atria and ventricles 						

Secondary Objective	
 Characterize physician feedback regarding the deployment, maneuverability, and signal quality acquired with the OPTRELL™ catheter for mapping in the atria and ventricles
Primary Endpoints	
 Safety: Incidence of serious adverse events within 7 days of index procedure related to the OPTRELL™ catheter Effectiveness: Completion of pre-ablation mapping requirements and clinically indicated mapping with the OPTRELL™ catheter without resort to non-study mapping catheter(s)
Secondary Endpoints	
 Physician assessment of deployment, maneuverability, and signal quality acquired with the OPTRELL™ catheter for mapping in the atria and ventricles Incidence of serious adverse events within 7 days of index procedure Incidence of non-serious adverse events within 7 days of index procedure associated with the use of the OPTRELL™ catheter
Study Population	
Subjects scheduled to have a clinically-indicated catheter mapping and ablation procedure for management of an arrhythmia in the following 5 subgroups:
 
Atrial procedures:
 
 Scar-related Atrial Tachycardia (AT; includes atypical atrial flutter), procedures resulting from previous atrial fibrillation ablation; Persistent Atrial Fibrillation (PSAF); Paroxysmal Atrial Fibrillation (PAF). 
Ventricular procedures:
 
 Ventricular Tachycardia (VT): ischemic and non-ischemic VT, cardiomyopathy and idiopathic VT. Premature Ventricular Complex (PVC)
Sample Size	
A sample size of 30 subjects will allow characterization of the performance and safety of the OPTRELL™ catheter. Approximately 20 atrial and 10 ventricular procedures will be performed.

Geographic areas to be included	
Up to 4 sites in Europe.

Study Duration	
Approximately 5 months enrollment and 7-day follow-up per subject

Visit Intervals	
Baseline/procedure, 7-day follow-up phone call or clinic visit after study procedure

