
Statistical Analysis
	
There will be no formal hypothesis testing on outcomes in this study. The safety and performance data below will be summarized with descriptive statistics.
 
Analysis for these endpoints will be performed overall, per chamber and separately for each arrhythmia subgroup.
 
Analysis for Primary Endpoints:
 
Mapping Performance
 
 - The number and proportion of subjects in whom pre-ablation mapping and clinically indicated mapping performed successfully with the OPTRELL™ catheter without resort to other mapping catheters. 
Safety
 
 - Serious Adverse Events related to the OPTRELL™ catheter during the 7-day follow-up period 
Analysis for Secondary Endpoints:
 
Physician Feedback
 
 - Physician feedback on the catheter deployment, maneuverability, and signal quality acquired with the OPTRELL™ catheter for mapping in the atria and ventricles using a physician-completed survey, using a Likert scale of 1 to 7 (1=poor and 7=excellent) will be summarized and listed for the study population, by chamber,

	
by subgroups and by catheter configuration.
 
Procedural characteristics will include, but are not limited to:
 
 - Pre-ablation mapping: 
 o Pre-ablation mapping duration with the OPTRELL™ catheter (i.e. time between first and last mapping point prior to first ablation point) by chamber and arrhythmia subgroup. o Mapping algorithms used (e.g. voltage map, LAT, etc.) o CARTO® 3 modules used o Types of areas of interest captured with the OPTRELL™ catheter (e.g. PV triggers, previous PVI lesion gaps, ventricular scar slow conduction zone, critical isthmus for atypical flutter, etc.) in pre-ablation mapping. o Mapping density. - Total procedure time. 
Safety
 
 - All Serious Adverse Events during the 7-day follow-up period - All non-serious Adverse Events related to the OPTRELL™ catheter during the 7-day follow-up period

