8.1 Description of the Study Design

This study is a prospective, single arm, non-randomized, open-label, multi-center study. Thirty subjects will be enrolled.

Subjects meeting the inclusion / exclusion criteria and who sign the informed consent form (ICF) will be enrolled in this study. The clinical investigation is targeting approximately 4 sites in Europe.

This study will serve to characterize the feasibility and safety of using the OPTRELL™ catheter in procedures for subjects in five different arrhythmia subgroups (Complex AT/re-do AF, PsAF, PAF, VT and PVC). Subjects will be treated per investigator's standard of care and followed until 7 days post-procedure.

Planned analyses are described in the Statistical Analysis section (20.0) of this clinical investigational plan.

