8.2.3 Additional Endpoints

Additional procedural characteristics, including but not limited to:

- Pre-ablation mapping time
 - o Pre-ablation mapping duration with the OPTRELL™ catheter (i.e. time between first and last mapping point prior to first ablation point) by chamber and arrhythmia subgroup
 - o Mapping algorithms used (e.g. voltage map, LAT, etc.)
 - o CARTO® 3 modules used
 - o Types and of areas of interest captured with the OPTRELL™ catheter (e.g. PV triggers, previous PVI lesion gaps, ventricular scar slow conduction zone, critical isthmus for atypical flutter, etc.) in pre-ablation mapping
 - o Mapping density
- Total procedure time

9. Study Population

The study population consists of subjects scheduled to have a clinically-indicated catheter mapping and ablation procedure for management of one the following arrhythmia:

- 1) Scar-related Atrial Tachycardia (AT; includes atypical atrial flutter), procedures resulting from previous atrial fibrillation ablation;
- 2) Persistent Atrial Fibrillation (PsAF);
- 3) Paroxysmal Atrial Fibrillation (PAF).
- 4) Ventricular Tachycardia (VT): ischemic and non-ischemic VT, cardiomyopathy and idiopathic VT.
- 5) Premature Ventricular Complex (PVC)

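### PVC is a planned subgroup separate from VT, but inclusion criteria 1 and 2 name only VT, AT or AF, so a PVC-only subject is literally ineligible

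*Combined protocol and SAP*

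**What the plan says.** **Population and subgroups.** The synopsis (Section 5) describes subjects scheduled for mapping and ablation "for management of an arrhythmia in the following 5 subgroups", of which VT is the fourth and PVC the fifth. Section 8.1 repeats "five different arrhythmia subgroups (Complex AT/re-do AF, PsAF, PAF, VT and PVC". Section 9 lists PVC as item 5, and its VT item covers ischemic, non-ischemic, cardiomyopathy-related and idiopathic VT without mentioning PVC. Section 20.4.2, part of the statistical plan, has subjects enrolled into the same five groups.

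**Eligibility.** Section 9.1 opens with "Candidates for this study must meet ALL of the following criteria". Criterion 1 requires a candidate for mapping and ablation "for the management of ventricular tachycardia, atrial tachycardia or atrial fibrillation". Criterion 2 adds: "At least one episode of the targeted arrhythmia (ventricular tachycardia, atrial tachycardia or atrial fibrillation) must have been documented". The synopsis carries the same two criteria.

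**Consequences of ineligibility.** Section 14.1 screens against the inclusion and exclusion criteria. Section 17 gives departure from those criteria as an example of a protocol deviation and forbids waivers. Under Sections 10.2 and 10.3, a subject found ineligible before catheter insertion is excluded and may be replaced.

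**Analysis.** In Section 20.3 the Safety set needs only catheter insertion, while the PP set also needs the eligibility criteria to be met and mapping to be started. Section 20.4.7 summarizes primary effectiveness in PP, with the success proportion per chamber and overall. The synopsis promises more: "Analysis for these endpoints will be performed overall, per chamber and separately for each arrhythmia subgroup".

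**The concern.** The plan sets up a subgroup that its own mandatory criteria do not admit. A site that follows the subgroup lists and enrols a PVC-only subject commits a deviation under the written criteria. A site that follows the criteria cannot enrol one at all. The PP set depends on eligibility, so the same mismatch also decides who counts towards the primary effectiveness endpoint.

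Two things are at stake. The first is coverage: one of five planned arrhythmia groups could end with no PVC-only subjects, in a first-in-human study meant to characterize the catheter across arrhythmia types. The second is a consistent PP denominator: sites ("Up to 4 sites in Europe") and the analyst could each settle the question differently, with no written rule to decide between them.

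**Working it through.** The plan has no figure to reproduce here. Section 20.2 bases 30 subjects on previous experience, with no power or precision calculation. The check is a comparison of texts, followed by simple subtraction.

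**Step 1. Can a PVC-only subject meet the criteria?** Both criteria name VT, atrial tachycardia (AT) and atrial fibrillation (AF). The parenthesis in criterion 2 is a closed list, not a set of examples. Sections 5 and 9 spell out VT and then list PVC separately, and no section says that VT includes PVC. As written, the answer is no. A subject with PVCs whose documented ablation target also includes VT, AT or AF can qualify, so the point is confined to PVC-only subjects.

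**Step 2. What follows under each way of applying the text?** Inputs: 30 subjects in total, about 20 atrial and 10 ventricular procedures (Section 20.2). Let k be the number of PVC-only subjects. The documents give no VT/PVC split, so k is an unknown with arithmetic bounds 0 to about 10. Everyone else is assumed to qualify for PP.

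- *Excluded before insertion.* PVC-only subjects are screened out, or excluded and replaced. There are 0 PVC-only subjects in the Safety set and 0 in PP. The total of 30 and the approximate 20/10 split can still be reached with other subjects, so the denominators need not shrink.
- *Treated as an eligibility deviation.* Safety = 30; overall PP = 30 − k; ventricular PP = 10 − k; share of all subjects lost from PP = k/30.
- *Broad reading, with VT taken to cover PVC.* Safety = 30, overall PP = 30 and ventricular PP = 10 for every k.

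| k | Overall PP, deviation | Ventricular PP, deviation | Share lost | Overall / ventricular PP, broad |
|---|---|---|---|---|
| 0 | 30 | 10 | 0/30 = 0% | 30 / 10 |
| 5 | 30 − 5 = 25 | 10 − 5 = 5 | 5/30 = 16.7% | 30 / 10 |
| 10 | 30 − 10 = 20 | 10 − 10 = 0 | 10/30 = 33.3% | 30 / 10 |

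The deviation and broad readings differ by exactly k in each denominator.

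**Step 3. Which analyses are touched?**

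- Primary safety uses the Safety set, so the deviation route leaves it unchanged. The exclusion route leaves no PVC-only subjects in its by-subgroup summary.
- Primary effectiveness (Section 20.4.7), general procedure data (20.4.6) and physician feedback (20.4.8) use PP and lose the k subjects under the deviation route.
- For procedural parameters, Section 20.4.8 names the PP set but then gives as denominator the subjects in whom mapping was started, without an eligibility condition. The text does not settle whether PVC-only deviations count there.

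**The case against.** The strongest reply is that the intent is plain. Section 9, the parent of 9.1, puts PVC in the population, and Section 20.4.2 says that subjects will be enrolled into that group. An analyst who removed every PVC subject from PP would empty a subgroup that the same plan creates. The LVEF exclusions in Section 9.2 pair VT patients with atrial-arrhythmia patients, which may hint that VT was used as shorthand for the ventricular group. Sponsor training and clarification (Section 18.1.1) and monitoring make divergence between sites less likely. Section 20.4.3 reports eligibility failures and analysis-set counts, so a loss from PP would probably be visible in the report.

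Much of this stands. Intent to enrol PVC is written, and the mismatch looks like a drafting omission. But intent does not amend a mandatory criterion where waivers are forbidden. The shorthand reading is only an inference, since the same exclusions fit equally well with PVC never having been carried into the eligibility section. Nothing shows that training addresses the point. Visibility in the report would reveal the loss without curing it.

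A reader might infer that any literal application shrinks the ventricular and overall effectiveness denominators. The documents do not support that: subjects excluded before insertion can be replaced, so the shrinkage belongs to the deviation route alone. A reader might also take the 33.3% as an expected loss. It is only an upper bound, and it would require every ventricular subject to be PVC-only although VT is itself a planned subgroup.

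**Conclusion.** The contradiction stands and should be corrected. As written, the plan gives a PVC-only subject no compliant route into primary effectiveness, whatever the number of such subjects.

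The size depends on how the text is applied. With exclusion before insertion, the plan loses its PVC-only subjects for both safety and effectiveness, while the total and the approximate split can be kept. With treatment as a deviation, the overall and ventricular PP denominators each fall by k, between 0 and about 10, and primary safety is unaffected. Under the broad reading nothing is lost, but that reading is nowhere stated. These figures assume 30 subjects, 10 of them ventricular, with all others qualifying for PP.

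A reader might go further and infer that a primary analysis would fail, or that the sponsor meant to keep PVC subjects out. Neither is supported. Section 20.1 plans no formal inference, no precision target is set, and Section 20.2 disclaims clinical claims of effectiveness; the subgroup lists point towards PVC being in scope. The harm is the loss of a planned subgroup or an inconsistent PP denominator.

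**What to change.** Reconcile inclusion criteria 1 and 2 (Sections 5 and 9.1) with the population and subgroup lists (Sections 5, 8.1, 9 and 20.4.2), so that both include PVC or both omit it. Which of the two is for the sponsor to decide. Once they agree, the eligibility condition in the PP definition treats PVC subjects the same way at every site and in the analysis.

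The cost is a wording amendment, with no extra patients or procedures. It also needs the approvals in Sections 16.1 and 17: an amendment goes back to those who approved the original protocol, and only administrative changes that leave the benefit-risk balance untouched have an abbreviated route. A change to eligibility may not qualify for that route, so time for ethics committee and competent authority approval should be allowed.

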9.2 Participant Exclusion Criteria

Candidates will be excluded if ANY of the following criteria apply:

1. Diagnosed with an arrhythmia requiring epicardial mapping
2. Study arrhythmia secondary to reversible cause, or secondary to electrolyte imbalance, thyroid disease, or non-cardiac cause
3. Atrial arrhythmias: patients with a left atrial size >55 mm
4. LVEF \leq 25% for VT patients
5. LVEF \leq 40% for patients with atrial arrhythmia
6. Documented intracardiac thrombus as detected on imaging
7. Contraindication to anticoagulation (i.e. heparin, warfarin, dabigatran)
8. History of blood clotting or bleeding abnormalities (e.g. hypercoagulable state)
9. Myocardial infarction within the past 2 months (60 days)
10. Documented thromboembolic event (including TIA) within the past 12 months (365 days)
11. Uncontrolled heart failure or NYHA function class IV
12. Implanted with a pacemaker or intracardiac cardiac defibrillator within the past 6 weeks (42 days)
13. Implanted with a prosthetic valve
14. Active illness or active systemic infection or sepsis.
15. Diagnosed atrial or ventricular myxoma, interatrial baffle or patch, tumor or other abnormality that precludes catheter introduction or manipulation.
16. Significant congenital anomaly or medical problem that in the opinion of the investigator would preclude enrollment in this study.
17. Subjects that have ever undergone a percutaneous or surgical valvular cardiac procedure (i.e., ventriculotomy, atriotomy, and valve repair or replacement and presence of a prosthetic valve)
18. Any cardiac surgery within the past 60 days (2 months) (includes PCI)
19. Atrial septal closure within the past 6 weeks (42 days)
20. Presence of a condition that precludes vascular access
21. Women who are pregnant (as evidenced by pregnancy test if pre-menopausal), lactating, or who are of childbearing age and plan on becoming pregnant during the course of the clinical investigation.
22. Categorized as vulnerable population and requires special treatment with respect to safeguards of well-being

23. Concurrent enrollment in an investigational study evaluating another device or drug.

10. Participant Withdrawal or Termination

10.1 Reasons for Withdrawal or Termination

Participants are free to withdraw from participation in the study at any time upon request without penalty or loss of benefits to which they may otherwise be entitled. Participants will be informed prior to study entry that they are free to withdraw from the study at any time and for any reason without prejudice to their future medical care by a physician or the institution.

An investigator may terminate a subject's participation in the study if:

- Any clinical AE, laboratory abnormality, or other medical condition or situation occurs such that continued participation in the study would not be in the best interest of the participant
- Withdrawal is in the subjects' best interest
- Subject withdraws consent
- Subject is lost to follow-up

Every subject should be encouraged to remain in the study until they have completed the protocol required follow-up period.

10.2 Handling of Participant Withdrawals or Termination

If a subject is removed or withdraws from the study, the date and reason for withdrawal will be recorded on the appropriate electronic Case Report Form (eCRF). If the subject is withdrawn due to an AE or SAE, the Investigator should follow the subject until the AE/SAE has resolved or is considered stable.

If a subject is unable to return for an office/clinic visit or cannot be contacted by telephone, 3 separate telephone calls should be made to obtain subject related safety information. All attempts should be documented in the source documents. If the subject does not respond to the 3 telephone calls, then the investigator must send a certified letter to the subject. If the subject does not respond to the letter, then the subject will be considered "lost to follow-up" for the study.

Subjects who have signed the ICF, but are later found not to be eligible PRIOR to insertion of the study catheter can be replaced. Replacement subjects will be recruited and enrolled following the same procedures as non-replacement subjects.

10.3 Subject Disposition

- **Enrolled Subjects:** Patients who sign the ICF.
- **Excluded Subjects:** Subjects who are enrolled but never undergo insertion of the study catheter. Excluded subjects will be subjected to safety event reporting between ICF signature and date of exclusion. Subjects who signed the ICF but are found to be ineligible prior to insertion of the catheter are also considered as excluded.
- **Discontinued Subjects:** Enrolled subjects who have the study catheter inserted but no mapping points are taken with it. Discontinued subjects will remain in follow-up for 7 days for safety evaluation.

- **Lost to Follow-up Subjects:** Enrolled subjects of which contact is lost after most recent visit (despite 3 documented attempts to contact the subject).
- **Withdrawn / Early Termination Subjects:** Subjects who withdraw consent for study participation or are withdrawn by the investigator, are terminated from the study prior to completion of all follow-up visits.
- **Completed Subjects:** Enrolled subjects who have not been excluded, discontinued, withdrawn, terminated early, or lost-to-follow-up from the study prior to the final study visit.

11. Responsibilities

11.1 Investigator Responsibilities

Investigators at each participating clinical site will have the following responsibilities:

- Assuring compliance by site personnel with the provisions of the protocol
- Providing the Sponsor with:
 - Signed, dated Investigator Agreement
 - Written Ethics Committee (EC) approval letters and EC-approved consent forms
 - Signed, dated Financial Disclosure form for each participating investigator
 - Curriculum vitae for each investigator
- Maintain an accurate and current Delegation of Authority log which identifies individuals authorized to perform work for the study and assuring compliance by site personnel with the provisions of the protocol
- Completing the appropriate training on the device and the study protocol prior to enrolling and using the catheter in subjects
- Maintain accurate and current logs for the study such as:
 - Subject log, Device Accountability Log
- Obtain initial and amendment (if applicable) EC approval and annual review/approval thereafter for the study protocol and informed consent as applicable
- Obtain ICF and enroll patients
- Perform medical procedures
- Order tests required by the study protocol
- Follow subjects until the end of the study protocol
- Accurately complete and sign eCRFs in a timely manner
- Maintain relevant source documentation and allow Sponsor direct access to perform monitoring or auditing duties
- Maintain records and provide reports according to prevailing regulatory requirements
- Share relevant study-related information with delegated study staff
- Inform the appropriate entities (e.g., Sponsor, Competent Authority (CA), EC) in a timely manner regarding the occurrence of AEs and/or product malfunctions.
- Making sufficient effort to maintain contact with treated subjects who fail to comply with the follow-up requirements

- Maintain study records for at least 5 years or as specified per country specific record retention requirements after the study is completed and or terminated. The Sponsor will notify the Investigator of either of these events.
- Complying with EC and Sponsor annual report requirements, including the final report.

11.2 Sponsor Responsibilities

The Sponsor (Biosense Webster, Inc.) will be responsible for the following:

- Conduct of pre-study site assessment and approval
- Preparation and modification (if applicable) of study documents including but not limited to the protocol, CRFs and informed consent
- Selection of appropriately qualified and trained individuals, including monitors, to conduct the study
- Conduct protocol and device training for investigators and research personnel as applicable
- Set-up of study-specific committees (if applicable).
- Obtain signed study contracts from investigators/hospitals, Clinical Research Organizations (CROs) and other involved parties
- Ship study devices to each site
- Monitor sites for the duration of the study
- Maintain study database
- Inform investigator of his/her responsibilities
- Submit and obtain approval for study from applicable regulatory agencies
- Preparation of reports summarizing the status of the study no less than annually. These reports will be supplied to the PI at each site.
- Update Report of Priors, IFU, IB, and Risk Analyses, as applicable
- Update investigators on safety issues, if needed
- Report (including AE's and DDs) to study investigators and regulatory agencies, as required
- Have relevant safety information reviewed by the Study Safety Lead, as required
- Communications with the CA
- Submission of any amendments to the Clinical Study Protocol/Investigational Plan to the CA.

12. Study Device Description

